#### **4.4.1.3 Supportive Analyses**

If there is a difference of 10% or more in the overall number of subjects between PP and mITT populations, a summary of the primary efficacy variable will be presented for all subjects in the PP population ([Table 14.2.2.2.1](#)), mean and SE will be presented graphically over time ([Figure 14.2.1.2](#)) and the same ANCOVA model applied to the primary analysis will be performed on the PP population ([Table 14.2.2.2.2](#)).

#### **4.4.2 Secondary Efficacy Variables**

##### **4.4.2.1 Number of Bleeding Sites at Week 6 and Week 12**

The number of bleeding sites for each subject is the number of sites with a BI value of 1 or 2. The BI scoring system is described in [Section 4.4.1.1](#).

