## Type and Planned Number of Subjects

Sufficient subjects will be screened to randomize approximately 150 (maximum 175) to ensure approximately 128 evaluable subjects complete the entire study. Subjects will be generally healthy, have mild-moderate generalized plaque-induced gingivitis at Baseline and wear one conventional RPD.

The modified intent to treat (mITT) population (defined as those subjects who are randomized, receive at least one dose of study product and have at least one post-baseline efficacy measurement performed) will be used for all primary and secondary analyses. The primary efficacy endpoint will be the Bleeding Index (BI) score after 12 weeks of study treatments. The BI score will be calculated as the average index over all tooth sites. An analysis of covariance (ANCOVA) model will be used for the primary analysis with treatment, gender, denture material type (acrylic or cobalt/chrome), and the baseline mean overall MGI score (low:  $\leq 2.0$ ; high  $> 2.0$ ) as factors and the baseline BI score as a covariate. The adjusted means of the two

treatments and the treatment difference will be provided together with 95% CI and P-values. The proportionate reduction will be calculated for BI and MGI endpoints.

The null and alternative hypotheses to be tested in the primary analysis are;

$H_0$ : There is no treatment difference in mean BI score after 12 weeks

$H_1$ : There is a treatment difference in mean BI score after 12 weeks

Secondary efficacy endpoints will be:

- Number of bleeding sites at Week 6 and Week 12
- MGI score at Week 6 and Week 12
- Overall TPI score at Week 6 and Week 12
- PDCI score at Week 6 and Week 12
- Interproximal TPI score at Week 6 and Week 12
- Overall calculus and oral debris scores and the composite OHI score at week 6 and week 12
- BI score at Week 6

The BI score, MGI score, OHI score (and individual scores of calculus and oral debris) and overall TPI scores will be calculated as the average index values over all tooth sites. The interproximal TPI score will be calculated as the average index value over all interproximal tooth sites. The number of bleeding sites will be calculated as the number of tooth sites with a BI score of 1 or 2. The PDCI will be calculated as the average index values over all subjects.

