## 5.2 Inclusion Criteria

Subject eligibility should be reviewed and documented by an appropriate member of the investigator's study team before subjects are included in the study.

An individual must meet all the following inclusion criteria to be eligible for enrollment into the study:

1. Subject provision of a signed and dated informed consent document indicating that the subject has been informed of all pertinent aspects of the study before any assessment is performed.
2. Subject is male or female who, at the time of screening, is between the ages of 18 and 75 years, inclusive.
3. A subject who is willing and able to comply with scheduled visits, treatment plan, and other study procedures.
4. A subject with good general and mental health with, in the opinion of the investigator or medically qualified designee no clinically significant or relevant abnormalities in medical history or upon oral examination, or a condition, that would impact the subject's safety, wellbeing or the outcome of the study, if they were to participate in the study.
5. A subject who is a cell phone owner with text messaging capabilities.
6. Dental Criteria:
  - a. A subject with a minimum of 4 natural teeth in each arch.
  - b. A subject with a minimum of 30 scorable surfaces for MGI, BI, OHI and TPI.  
 (A scorable surface is defined as a surface that has at least 2/3 of the surface gradable for each clinical index. Third molars, orthodontically banded/bonded, fully crowned or extensively restored or grossly carious teeth are not included in the tooth or scorable surface count. *Third molars can be included if, as a result tooth loss, they are functioning as second molars.* Tooth surfaces with calculus deposits which, in the opinion of the clinical examiner, would interfere with the assessments of the selected clinical indices are also excluded.)
  - c. A subject with a minimum of 2 scorable abutment teeth, defined as teeth proximal to the RPD or impinged by an RPD clasp or rest.
  - d. A subject with generalized mild-moderate plaque-induced gingivitis present at the screening visit (in the opinion of the clinical examiner from a gross visual examination).
  - e. A subject with a mean whole mouth BI  $\geq 0.1$  to  $\leq 1.3$ , a mean whole mouth MGI  $\geq 1.75$  to  $\leq 2.30$  and a mean overall TPI score  $\geq 1.5$  at the Baseline visit.

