#### **12.2.6.1 Number of bleeding sites at Week 6 and Week 12**

Number of bleeding sites will be calculated as the average number of sites with a BI score of 1 or 2. At each post-baseline visit, the average number of bleeding sites will be analyzed using an ANCOVA model with treatment, gender, denture material type (acrylic or cobalt chrome), and baseline mean overall MGI score (low, high) as factors and the baseline score as a covariate. The adjusted means of the two treatments, the proportionate reduction for each treatment group, and the treatment difference will be provided together with 95% CI and P-values.

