## 4.4 Analysis of Efficacy

### 4.4.1 Primary Efficacy Endpoint

#### 4.4.1.1 Primary Efficacy Endpoint Definition

The primary efficacy endpoint is the BI score at Week 12. The BI score for each subject will be calculated as the average index value over all tooth sites scored as follows:

- BI Score = Sum of index values over all evaluable tooth sites/Number of evaluable tooth sites.

The BI score has a range of 0 to 2.

The BI will be assessed on the facial and lingual gingival surfaces of each scorable tooth. Three scores should be recorded buccally/labially (distal, body, mesial sites) and three scores lingually/palatally (distal, body, mesial sites). The BI will be assessed by the same examiner on all evaluable teeth at Baseline (Visit 2), Week 6 (Visit 3) and Week 12 (Visit 4).

The BI scoring system is described in [Table 4-2](#).

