#### **4.5.1.1 Number of Bleeding Sites at Week 6 and Week 12**

At each post-baseline visit, the average number of bleeding sites will be analyzed using an ANCOVA model with treatment group, gender, denture material type (acrylic or cobalt chrome), and baseline mean overall MGI score (low, high) as factors and the baseline number of bleeding sites as a covariate. The adjusted means and SEs of the two treatment groups together with the treatment difference, SE, 95% confidence interval of the difference, between-group p-value and the proportionate reduction will be provided in [Table 14.2.3.1.2](#) for the mITT population.

The proportionate reduction will be calculated as:

- Proportionate reduction =  $[(\text{Adjusted Mean of No Intervention Group} - \text{Adjusted Mean of Intervention Group}) / \text{Adjusted Mean of No Intervention Group}] * 100$ .

Descriptive statistics (n, mean, SD, SE, median, minimum, maximum) of the number of bleeding sites will be provided at Baseline, Week 6 and Week 12 visits by treatment group (and overall for Baseline only) for the mITT population ([Table 14.2.3.1.1](#)).

The raw mean and SE of the number of bleeding sites (whole mouth and associated with abutment teeth) will be presented graphically over time for each treatment group in [Figure 14.2.2](#) (mITT population).

The number of bleeding sites will be listed by subject and visit in [Listing 16.2.6.6.1](#) for all randomized subjects.

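### The bleeding-sites count is analysed without adjusting for the number of evaluable sites, and is also called an undefined average: a small, easily recovered loss of precision on a secondary endpoint

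*SAP*

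**What the plan says.** The definition in SAP 4.4.2.1 is a count: "The number of bleeding sites for each subject is the number of sites with a BI value of 1 or 2". The Protocol Summary agrees: "The number of bleeding sites will be calculated as the number of tooth sites with a BI score of 1 or 2". The abutment version in SAP 4.4.3.3 is built the same way.

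The model text in SAP 4.5.1.1 describes the outcome differently: "At each post-baseline visit, the average number of bleeding sites will be analyzed using an ANCOVA model". Its covariate is nevertheless "the baseline number of bleeding sites as a covariate". Protocol 12.2.6.1 also uses the average wording: "Number of bleeding sites will be calculated as the average number of sites with a BI score of 1 or 2". No divisor is given in either place, and SAP Table 5-1, which lists departures from the protocol, does not mention the difference.

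The primary endpoint does have a denominator (SAP 4.4.1.1): "BI Score = Sum of index values over all evaluable tooth sites/Number of evaluable tooth sites". MGI, TPI, CI and ODI are likewise divided by evaluable sites or surfaces.

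**The concern.** Partial-denture wearers differ by design in how many teeth they have left. With six BI sites per tooth, two subjects with the same bleeding rate can have quite different counts. That variation says nothing about treatment, and the model removes only the part carried by the baseline count. The number of evaluable sites follows directly from the site-level BI data, so leaving it out gives up precision that could be had for almost nothing.

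The set of scorable sites can also change between visits. A tooth lost or crowned removes up to six sites. Protocol 5.2 excludes surfaces where calculus "would interfere with the assessments of the selected clinical indices are also excluded", and some of these could become scorable after the Visit 2 prophylaxis. Neither document has a rule for a site that is scorable at one visit and not at another.

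Separately, the average wording leaves room for two programmers to build different outcome variables for the same endpoint.

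**Working it through.** **Plan's own figure.** There is none for this endpoint. The overall target is about 128 evaluable subjects, equally allocated, so 64 per arm. The sample-size basis is redacted and is not checked here.

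**Range of evaluable sites.**
- BI is scored at 3 buccal and 3 lingual sites, so 6 per tooth (SAP 4.4.1.1).
- Entry requires at least 4 teeth per arch and at least 30 scorable surfaces (Protocol 5.2, criteria 6a and 6b).
- OHI is scored on two surfaces per tooth, so 30 surfaces points to 30 / 2 = 15 teeth, or 15 × 6 = 90 sites.
- If *surface* were read as *site*, the floor would be 8 teeth, or 8 × 6 = 48 sites.
- With an assumed maximum of 27 teeth (162 sites), the spread is 162 / 90 = 1.8-fold on the first reading and 162 / 48 = 3.4-fold on the second.
- Abutment analyses may start from 2 scorable teeth (criterion 6c), or 12 sites.

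**Precision.** Simulated ANCOVA with 64 per arm, two-sided 0.05, and 4,000 trials per scenario. Assumed, not in the documents: control mean bleeding proportion 0.30 at baseline and 0.22 at follow-up; between-subject SD 0.12 and 0.10; 22% relative reduction; teeth uniform over the stated range; no site loss, so the baseline and follow-up site numbers coincide. Gender, denture material and the MGI factor were left out.

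Variance saved = 1 − (SD of estimate with evaluable sites / SD without)².

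| Teeth | Baseline–follow-up correlation | SD, count model | SD, with evaluable sites | Variance saved | Power: count / with sites / proportion |
|---|---|---|---|---|---|
| 15–27 | 0.3 | 2.319 | 2.289 | 2.5% | 71.5 / 73.4 / 74.8% |
| 15–27 | 0.5 | 2.097 | 2.093 | 0.3% | 79.6 / 80.0 / 81.4% |
| 15–27 | 0.7 | 1.859 | 1.867 | none | 89.2 / 89.1 / 89.6% |
| 8–27 | 0.3 | 2.036 | 1.938 | 9.4% | 67.0 / 70.8 / 74.6% |
| 8–27 | 0.5 | 1.894 | 1.847 | 5.0% | 73.8 / 76.1 / 78.8% |
| 8–27 | 0.7 | 1.609 | 1.604 | 0.6% | 85.9 / 86.5 / 87.8% |

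The simulation error of a power figure near 70% is √(0.7 × 0.3 / 4,000) = 0.7 points, so the smallest differences are noise. Further runs gave variance savings of about 1–8% for 8 to 24 teeth and about 3–9% for 2 to 6 abutment teeth.

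**Lost sites.** One lost six-site tooth lowers a subject's expected follow-up count by 6 × 0.22 = 1.3 with no clinical change. If a share d of the intervention arm alone loses one tooth, the between-arm bias is 6 × 0.22 × d. That is 0.07, 0.13 and 0.26 sites for d = 5%, 10% and 20%. The mean count is 0.22 × 6 × 17.5 = 23.1 and the standard error is about 1.9, so the largest of these is 0.26 / 1.9 = 0.14 standard errors. Over 8,000 null trials per scenario, type I error was 4.9–5.2% with one-sided loss. With equal loss of 5% or 10% it was 5.0–5.3%, with no bias beyond simulation error.

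**The case against.** The strongest reply is that the model does account for mouth size in part: the baseline count carries much of it, which is why the gain shrinks as the baseline–follow-up correlation rises. On the more natural reading of the 30-surface criterion the whole-mouth gain is close to nothing. A bleeding measure with a denominator is already primary, so the count is a complementary summary. All of this stands, and it limits the point to a minor one.

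A reader might infer that lost sites are scored as improvement and so favour the intervention. Within one subject the count does fall. The comparison is biased only if loss differs by arm, and the documents give no loss rate. Protocol 5.5.1 asks subjects to avoid elective dental procedures, so crowning within 12 weeks should be rare. Surfaces that become scorable after prophylaxis push counts up, not down, and both arms receive the prophylaxis. Calculus could re-form at different rates by arm, but nothing in the documents sizes this.

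A reader might also conclude that the endpoint should become a proportion, or that the evaluable-site number at each visit should be the covariate. The first would replace the endpoint named in the objectives. The second conditions on a variable measured after randomisation. The baseline number avoids both problems.

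**Conclusion.** The point holds as a small improvement. The count is the only tooth-site outcome with neither a denominator nor the number of evaluable sites in its model, and the average wording is an undefined inconsistency in both documents. That inconsistency is a matter of definition and does not itself cause any loss of precision.

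The size is a variance saving of about 0–3% for the whole mouth with 15 or more teeth, up to about 8% with 8 to 24 teeth (9.4% in the widest range simulated, 8 to 27), and about 3–9% for abutment teeth. These figures rest on assumed bleeding rates, correlations and tooth counts. The documents do not support a claim that the planned analysis is invalid, that its type I error is inflated, or that the primary BI result is affected.

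**What to change.** 1. Keep the count as the endpoint. Delete the word average in SAP 4.5.1.1 so that it matches SAP 4.4.2.1.
2. Add the baseline (Visit 2) number of evaluable BI sites as a covariate in the whole-mouth ANCOVA (SAP 4.5.1.1). Add the baseline number of evaluable abutment sites in the abutment ANCOVA (SAP 4.5.2.3).
3. Report bleeding sites divided by evaluable sites at the same visit as a supportive analysis. This also shows whether changes in scorable sites matter.
4. Record the added covariate, and the departure from the wording of Protocol 12.2.6.1, in SAP Table 5-1 before database lock.

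The cost is one degree of freedom per model, a supportive table and minor SAP wording. No new data are needed.

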##### **4.4.2.2 MGI Score at Week 6 and Week 12**

The MGI score for each subject will be calculated as the average index value over all tooth sites scored as follows:

- MGI Score = Sum of index values over all evaluable tooth sites/Number of evaluable tooth sites.

The MGI score has a range of 0 to 4.

The MGI will be assessed for the facial and lingual/palatal gingiva of all scorable teeth, four sites per tooth (facial surface - papilla and margin; lingual/palatal surface - papilla and margin).

The MGI will be assessed by the same examiner on all evaluable teeth at Baseline (Visit 2), Week 6 (Visit 3) and Week 12 (Visit 4).

The MGI scoring system is described in [Table 4-3](#).

**Table 4-3 The Modified Gingival Index**

Score	Description
0	Absence of inflammation
1	Mild inflammation: slight change in colour, little change in texture of any portion of the marginal or papillary gingival unit
2	Mild inflammation: criteria as [1] but involving the entire marginal or papillary gingival unit
3	Moderate inflammation: glazing, redness, edema, and/or hypertrophy of the marginal or papillary gingival unit
4	Severe inflammation: marked redness, edema and/or hypertrophy of the marginal or papillary gingival unit, spontaneous bleeding, congestion, or ulceration

#### 4.4.2.3 Overall TPI Score at Week 6 and Week 12

The Overall TPI score for each subject will be calculated as the average index value over all tooth sites scored as follows:

- Overall TPI Score = Sum of index values over all evaluable tooth sites/Number of evaluable tooth sites.

The TPI score has a range of 0 to 5.

Supra-gingival plaque will be assessed on the facial and lingual surfaces of all scorable teeth, six sites per tooth (three scores recorded buccally/labially [distal, body, mesial sites] and three scores lingually/palatally [distal, body, mesial sites]). The TPI will be assessed by the same examiner on all evaluable teeth at Baseline (Visit 2), Week 6 (Visit 3) and Week 12 (Visit 4).

The TPI scoring system is described in [Table 4-4](#).

**Table 4-4 The Turesky Plaque Index**

Score	Description
0	No plaque
1	Separate flecks of plaque at the cervical margin
2	Thin continuous band of plaque (up to 1 mm) at the cervical margin
3	Band of plaque wider than 1 mm but covering < 1/3 of the tooth surface
4	Plaque covering $\geq$ 1/3 but < 2/3 of the tooth surface
5	Plaque covering $\geq$ 2/3 of the tooth surface

#### 4.4.2.4 Interproximal TPI Score at Week 6 and Week 12

The Interproximal TPI score for each subject will be calculated as the average index value over all interproximal tooth sites (distal and mesial) scored as follows:

- Interproximal TPI Score = Sum of index values over all evaluable interproximal tooth sites/Number of evaluable interproximal tooth sites.

The TPI scoring system is described in [Section 4.4.2.3](#).

#### 4.4.2.5 BI score at Week 6

The BI score at Week 6 will be calculated in the same way as stated in [Section 4.4.1.1](#).

#### 4.4.2.6 CI score at Week 6 and Week 12

The Calculus Index (CI) score for each subject will be calculated as the average index value over all tooth surfaces scored as follows:

- CI Score = Sum of index values over all evaluable tooth surfaces/Number of evaluable tooth surfaces.

The CI score has a range of 0 to 3.

The CI will be assessed on the facial and lingual surfaces all scorable teeth. The CI will be assessed by the same examiner for all subjects throughout the study on all evaluable teeth at Baseline (Visit 2), Week 6 (Visit 3) and Week 12 (Visit 4).

The CI scoring system is described in [Table 4-5](#).

**Table 4-5 The Calculus Index**

Score	Description
0	No calculus present
1	Supragingival calculus covering not more than one third of the exposed tooth surface
2	Supragingival calculus covering more than one third but not more than two thirds of the exposed tooth surface or the presence of individual flecks of subgingival calculus around the cervical portion of the tooth or both
3	Supragingival calculus covering more than two thirds of the exposed tooth surface or a continuous band of subgingival calculus around the cervical portion of the tooth or both

#### 4.4.2.7 ODI score at Week 6 and Week 12

The Oral Debris Index (ODI) score for each subject will be calculated as the average index value over all tooth surfaces scored as follows:

- ODI Score = Sum of index values over all evaluable tooth surfaces/Number of evaluable tooth surfaces.

The ODI score has a range of 0 to 3.

The ODI will be assessed on the facial and lingual surfaces of all scorable teeth. The ODI will be assessed by the same examiner for all subjects at Baseline (Visit 2), Week 6 (Visit 3) and Week 12 (Visit 4).

The ODI scoring system is described in [Table 4-6](#).

**Table 4-6 The Oral Debris Index**

Score	Description
0	No debris or stain present
1	Soft debris covering not more than one third of the tooth surface, or the presence of extrinsic stains without other debris regardless of surface area covered
2	Soft debris covering more than one third, but not more than two thirds, of the exposed tooth surface
3	Soft debris covering more than two thirds of the exposed tooth surface

#### **4.4.2.8 OHI score at Week 6 and Week 12**

The OHI score is a composite of the CI and the ODI, calculated for each subject as the sum of the mean CI score and the mean ODI score.

The OHI score has a range of 0 to 6.

The CI score will be calculated as the average index value over all tooth surfaces scored, as described in [Section 4.4.2.6](#).

The ODI score will be calculated as the average index value over all tooth surfaces scored, as described in [Section 4.4.2.7](#).

#### **4.4.2.9 PDCI score at Week 6 and Week 12**

The PDCI score is reported as a single score for each subject based on the highest score of all surfaces of the RPD.

The PDCI score is an integer value with a range of 0 to 4.

All surfaces of the RPD should be assessed and the highest score applicable recorded. The PDCI will be assessed by the same examiner for all subjects at Baseline (Visit 2), Week 6 (Visit 3) and Week 12 (Visit 4).

The PDCI scoring system is described in [Table 4-7](#).

**Table 4-7 The Partial Denture Cleanliness Index**

Score	Description
0	No visible plaque; no matter adherent to the dental probe on light scraping
1	No visible plaque; matter adherent to the dental probe on light scraping
2	Deposits of plaque just visible on careful examination without need to confirm by scraping

3	Deposits of plaque clearly visible
4	Gross plaque deposits ("velvet appearance")

#### **4.4.3 Exploratory Efficacy Variables**

##### **4.4.3.1 Cleaning Perceptions Questionnaire scores at Week 6 and Week 12**

The cleaning perceptions questionnaire will be completed at Baseline (Visit 2), Week 6 (Visit 3) and Week 12 (Visit 4) to evaluate subject's perceptions of dental/denture cleaning.

The questionnaire consists 5 questions relating to general oral care and 2 questions relating to oral care routine.

At Baseline the questions will be scored from 1 to 4 (with a response of 1 indicating not at all confident/motivated/likely and a response of 4 indicating very confident/motivated/likely).

At Week 6 and Week 12 the questions will be in comparison to the period before the subject begins this study and will be scored from 1 to 5 (with a response of 1 indicating a lot less confident/motivated/likely, a response of 3 indicating no difference and a response of 5 indicating a lot more confident/motivated/likely).

The mean general oral care confidence at Week 6 and at Week 12 will be derived for each subject as the average score of question 12 to question 16.

At Baseline, 4 additional questions relating to the subject's attitude to oral care will be completed.

